16.2 Pharmacodynamics

NA.

16.3 Immunogenicity

Antidrug antibody (ADA) are assessed before the trial treatment infusion on Days 1, 15, 29, 43, 85, 127, 169. After Day 169, 1 sample (within 2 hours prior to infusion) every 12 weeks until the EOT visit and at the safety follow-up visit (30 days \pm 5 days after last treatment) for subjects receiving Avelumab once every 2 weeks. For 10 mg/kg once weekly cohort, ADA are assessed before the trial treatment infusion on Days 1, 15, 29, 43, 85, 127, 169, and then every 12 weeks while on treatment, and at the safety follow-up visit. If the sample is positive for ADA, it will be re-analyzed to determine the titer. The ADA results will be derived based on the algorithm as the following table.

Algorithm for the Derivation of ADA Results

Sample Screen Result	Confirmatory	Titer	ADA Result
Negative	NA	NA	Negative
NR	NA	NA	NR
Positive	Negative	NA	Negative
Positive	NR	NA	NR
Positive	Positive	Number	Number
Positive	Positive	NA	Positive-TNR

NR = no result, NA = not applicable, TNR = titer no result.

Negative, number, or positive-TNR are valid results while number and positive-TNR are considered as positive. Subjects will be characterized into different categories based on the below criteria.

Category	Definition	Subject at Risk (Denominator for Incidence)
Never positive	No positive results at any time point	Number of subjects with at least one valid result at any time point
Ever positive	At least one positive result at any time point	Number of subjects with at least one valid result at any timepoint
Pre-existing	A positive ADA result prior to treatment with Avelumab	Number of subjects with valid baseline result
Treatment boosted	A positive ADA result prior to treatment with Avelumab and the titer \geq 8*baseline titer while on avelumab treatment	Number of subjects with valid baseline and at least one valid post-baseline result
Treatment emergent	Not positive prior to treatment with avelumab and with at least one positive post-baseline result	Number of subjects with at least one valid postbaseline result and without positive baseline results (including missing, NR)

Transient positive	If treatment emergent subjects have (a single positive evaluation, or duration between first and last positive result <16 weeks) and last assessment not positive.	Number of subjects with at least one valid postbaseline result and without positive baseline results (including missing, NR)
Persistent positive	If treatment emergent subjects have duration between first and last positive result ≥16 weeks or a positive evaluation at the last assessment	Number of subjects with at least one valid postbaseline result and without positive baseline results (including missing, NR)

The frequency and percentage of each category will be presented by dose level/cohort and overall in tables based on Safety Analysis Set.

[figure not shown]
Listings of ADA results from ever positive ADA subjects will be prepared.

- Overview on ADA status: Subject ID, dose level, age, gender, ADA Status, Study Day of Start of ADA response, Duration of ADA immunogenicity response (weeks)
- Listing of ADA and Ctrough concentrations: Subject ID, dose level, age, Visit and Visit Date, ADA result, Date of last prior avelumab infusion, Days since last avelumab infusion, Date of last available predose drug concentration at or before ADA assessment and corresponding drug concentration
- Listing of all PK concentrations, Subject ID, dose level, age, Visit and Visit Date, Nominal time, observed avelumab serum concentration, Actual date/time; Hours since last avelumab infusion.
- Listing of immunogenicity data and adverse events (AEs): Subject ID, dose level, age, sex, study treatment start and stop date, all dates with positive ADA result, AE start date, stop date, preferred term, CTCAE toxicity grade, seriousness, and applicable flags for immune-related adverse event (irAE), infusion related reaction (IRR), serious adverse event (SAE), or reason for permanent treatment discontinuation.
- Listing of immunogenicity data and efficacy endpoints: Subject ID, dose level, age, start and stop of treatment, date of onset, time to onset (weeks since treatment start) and last date of ADA positive results, as well as date of onset, confirmed BOR and confirmed BOR date, DOR, PFS time or censoring time and reason for censoring, and OS time or censoring time and reason for censoring.

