**Planned number of subjects:**

Approximately 21 subjects (up to approximately 24 subjects).

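### SAP 16.3 puts baseline-negative subjects in the at-risk denominator for treatment-boosted ADA, so the percentage cannot exceed the share who were baseline-positive

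*SAP*

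**What the plan says.** SAP 16.3 sorts subjects into ADA categories and gives each category its own denominator, in a column headed "Subject at Risk (Denominator for Incidence".

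- **Treatment boosted, definition.** Two conditions apply: "A positive ADA result prior to treatment with Avelumab and the titer" must be at least "8*baseline titer while on avelumab treatment".
- **Treatment boosted, denominator.** "Number of subjects with valid baseline and at least one valid post-baseline result".
- **Treatment emergent, transient positive and persistent positive, denominator.** "Number of subjects with at least one valid postbaseline result and without positive baseline results (including missing, NR").
- **Valid and positive results.** "Negative, number, or positive-TNR are valid results while number and positive-TNR are considered as positive". Positive-TNR means a confirmed positive for which no titer was obtained.
- **Reporting.** "The frequency and percentage of each category will be presented by dose level/cohort and overall in tables based on Safety Analysis Set".

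Immunogenicity is a secondary objective, and ADA titer is a secondary endpoint (Protocol 4.2 and 8.3.2). Protocol 8.5.3.2 promises only a listing of ADA results with titers where applicable. Neither that section nor Protocol 7.7 explains or changes the boosted denominator.

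**The concern.** Only a subject who is ADA-positive before the first dose can be boosted. The stated denominator nevertheless admits everyone with valid results before and after dosing, whatever the baseline result. Each baseline-negative subject is therefore scored as at risk and not boosted.

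The three rows that follow work on the opposite principle: they drop baseline-positive subjects, who cannot have those events. Adjacent percentages in one table then answer different questions. The emergent row gives a rate among those who could have the event. The boosted row gives that rate multiplied by the share who were baseline-positive. A small boosted percentage may mean that avelumab rarely boosts existing ADA, or only that few subjects had any.

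Two further gaps sit in the same row. A positive-TNR result is valid but cannot enter an eight-fold titer comparison. The boosted row also limits the assessment to time on treatment, which 16.3 does not define, while the emergent row takes any post-baseline result.

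**Working it through.** The plan states no boosted percentage, so there is no figure to reproduce.

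**Inputs**
- N: subjects with valid results before and after dosing. The Protocol synopsis plans "Approximately 21 subjects (up to approximately 24 subjects"); I take all of them as evaluable, so N = 21 or 24.
- p: those of the N who are ADA-positive at baseline. The documents give no prevalence, so p = 1, 2 or 3 is assumed.
- b: boosted subjects, with b ≤ p. b = 1 is assumed.

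**Step 1: the identity.** The SAP reports b/N. Among subjects who can be boosted, the rate is b/p. Since b/N = (b/p) × (p/N), the reported figure is the at-risk rate scaled by p/N. Since b ≤ p, it cannot exceed p/N, even if every baseline-positive subject is boosted.

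**Step 2: the numbers for b = 1**

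| p | Cap p/N, N = 21 | Cap p/N, N = 24 | SAP figure 1/N | Among baseline-positive, 1/p |
|---|---|---|---|---|
| 1 | 4.8% | 4.2% | 4.8% or 4.2% | 100% |
| 2 | 9.5% | 8.3% | 4.8% or 4.2% | 50% |
| 3 | 14.3% | 12.5% | 4.8% or 4.2% | 33.3% |

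The SAP figure stays the same in every row, whatever share of the baseline-positive subjects was boosted. In a cohort of six it is 1/6 = 16.7%, again whatever p is.

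**Step 3: next to the emergent row.** Take N = 21, p = 2, b = 1, with one treatment-emergent subject among the other 21 − 2 = 19.
- Boosted, as planned: 1/21 = 4.8% (exact 95% CI 0.1% to 23.8%).
- Emergent, as planned: 1/19 = 5.3%.
- Boosted among baseline-positive: 1/2 = 50% (exact 95% CI 1.3% to 98.7%).

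The table would show 4.8% beside 5.3%, although one rate is 1 of 2 and the other 1 of 19. The wide interval around 50% shows that the corrected figure will itself carry little information.

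**Step 4: nobody baseline-positive.** With an assumed prevalence π, the chance that none of N is positive is (1 − π)^N. For π = 1%, 5% and 10% this is 81%, 34% and 11% at N = 21, and 79%, 29% and 8% at N = 24. The planned table would then print 0/N = 0%, although no subject could have had the event and the rate is not estimable.

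**Step 5: results that cannot be scored.** A positive-TNR baseline has no titer to multiply by eight. A subject with a numeric baseline whose only post-baseline results are positive-TNR has no titer to compare with it. Both meet the stated denominator, and the SAP gives no rule for either.

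**Step 6: the window.** SAP 16.3 places the follow-up ADA sample at 30 ± 5 days after last treatment, that is 25 to 35 days. Protocol 8.5.3.1 ends the on-treatment period 30 days after the last dose, or on the day before subsequent anticancer drug therapy if that is earlier. If that definition is borrowed, a sample at 25 to 30 days counts for boosting unless new drug therapy has begun. One at 31 to 35 days, or after new drug therapy starts, does not. The emergent row would accept all of these.

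**The case against.** The strongest defence is that the column heading is generic. It also covers the never-positive, ever-positive and pre-existing rows, and nobody is literally at risk of being never positive. Read that way, the boosted row is a share of all subjects evaluable before and after dosing, which is a legitimate summary. This stands in part: the share is usable if labelled as such. It does not explain why the next three rows are restricted to subjects who can have the event, or why the heading calls the figure an incidence.

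It is also true that little information is lost. The table gives counts, the pre-existing row gives the number positive at baseline, and ADA results of ever-positive subjects are listed. A careful reader could nearly rebuild b/p. No test or decision rule uses the percentage, and no comparison of the boosted and emergent rows is planned. This stands, and it sets the severity.

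A reader might go further in two ways that the documents do not support.
- **That a titer rise first seen at the 30-day follow-up visit is lost for boosting.** That takes treatment to end at the last dose. SAP 16.3 does not say so, Protocol 8.5.3.1 adds 30 days, and the adverse-event window in SAP 15.2 also runs to 30 days after the last dose. What can be said is that the phrase is undefined and that, under the protocol's period, some follow-up samples could fall outside.
- **That the plan dilutes the rate 6- to 24-fold.** Those factors are N/p for an assumed p of 4 down to 1 among 24 subjects. With no prevalence in the documents they are illustrations, and if nobody is boosted the planned figure is 0% whatever p is.

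**Conclusion.** The concern holds, as a minor point. The boosted denominator includes subjects who cannot meet the definition, so the reported percentage is the at-risk rate times p/N, is capped at the baseline-positive share, and rests on a different principle from the emergent, transient and persistent rows. This follows from the wording of SAP 16.3 alone. The size does not: 4.8% against 50% assumes N = 21, p = 2 and b = 1.

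The unscorable positive-TNR results and the undefined window are real gaps in the same row, but they support a clarification rather than a claim that data are lost. The documents do not support a reading that the immunogenicity conclusions would be misleading as a whole: this is one percentage in a descriptive secondary analysis of 21 to 24 subjects, with the counts and listings alongside.

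**What to change.** In SAP 16.3:

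1. Set the boosted denominator to subjects with a positive baseline ADA and a numeric titer who also have one or more post-baseline results that can be scored, meaning negative or a numeric titer.
2. Show subjects with a positive-TNR baseline, and those whose only post-baseline results are positive-TNR, as not evaluable for boosting.
3. Print n/N with each percentage, and write not estimable when N = 0.
4. If the share of all evaluable subjects is also wanted, keep it as a separate row under that label and not as incidence among those at risk.
5. State one assessment window for the boosted and emergent rows, for example any post-baseline sample.

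The cost is a few lines of SAP wording and the programming of one table row, with no new data. The corrected percentage will rest on very few subjects. By cohort its denominator will often be 0 or 1 if baseline positivity is uncommon, so the counts should be read before the percentage.

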ADA: antidrug antibody; AE: adverse event; CR: complete response; CT: computed tomography; D: Day; DLT: dose-limiting toxicity; ECG: electrocardiogram; ECOG PS: Eastern Cooperative Oncology Group performance status; EOT: End-of-Treatment; hCG: human chorionic gonadotropin; HIV: Human immunodeficiency virus; ICF: Informed consent form; IMP: investigational medicinal product; MRI: magnetic resonance imaging; PD: progressive disease; CCI: [redacted] PK: pharmacokinetics; PR: partial response; RECIST: response evaluation criteria in solid tumors; SAE: serious adverse event; T4: thyroxine; TSH: thyroid-stimulating hormone; V: Visit; W: Week.

1. A time window of up to 3 days before or 1 day after the scheduled visit day (- 3/+ 1 days) is permitted for all study procedures (except for PK sampling visits on Day 2 and 3, see [Table 1-3](#)). The calculation of the dose of avelumab will be based on the weight of the subject determined within 72 hours prior to the day of drug administration.
2. All subjects will have an EOT Visit within 7 days after the decision to discontinue avelumab. In addition, subjects will be followed every 12 weeks ( $\pm 7$  days) for survival (including assessment of any further anticancer therapy).

CCI

[figure not shown]
4. If another anticancer therapy is administered before the end of this 7-day period, the EOT Visit should be conducted prior to the start of this new therapy, if possible. The EOT Visit may be performed on the day of the decision to discontinue avelumab.

CCI

7. Medical history should include history of cancer, previous and ongoing medications, previous surgeries, radiotherapies, baseline medical conditions, smoking and alcohol history, and family cancer history.
8. A full physical examination will be conducted at Clinical Screening, at the EOT Visit and at the 30-day Safety Follow-up Visit. During the Treatment Phase, the physical examination will be symptom-directed.
9. If the Clinical Screening ECOG PS was performed within 3 days prior to Day 1, it does not have to be repeated at Visit 1/Cycle 1 Day 1.
10. Enrolment will be done after confirmation that the subject meets all screening inclusion criteria ([Section 5.3.1](#)) without matching any exclusion criterion ([Section 5.3.2](#)).

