9.3.3 Definition of Duration

Duration will be calculated by the difference of start and stop date + 1, unless otherwise specified.

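### SAP 16.3 classes a subject as transient ADA-positive when the last sample has no result, and counts boosted titers over an undefined window that does not match its own denominator

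*SAP*

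**What the plan says.** SAP 16.3 derives an ADA result for each sample and then puts subjects into categories.

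- **Valid and positive results.** "Negative, number, or positive-TNR are valid results while number and positive-TNR are considered as positive". NR is in neither group.
- **Transient positive.** A treatment-emergent subject with one positive result, or with "duration between first and last positive result <16 weeks) and last assessment not positive". The last-assessment condition applies to both alternatives.
- **Persistent positive.** A treatment-emergent subject with "duration between first and last positive result ≥16 weeks or a positive evaluation at the last assessment".
- **Denominator for both.** Subjects with a valid post-baseline result and "without positive baseline results (including missing, NR").
- **Treatment boosted.** A subject positive at baseline whose titer reaches at least "8*baseline titer while on avelumab treatment". The denominator is subjects with a valid baseline result and at least one valid post-baseline result.
- **Treatment emergent.** Any positive post-baseline result, with no restriction to the treatment period.

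On dates, SAP 9.3.3 states: "Duration will be calculated by the difference of start and stop date + 1, unless otherwise specified". SAP 16.3 does not say whether the 16 weeks are counted on actual or scheduled dates.

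**The concern.** The transient and persistent definitions are exact complements, so the last-assessment test assigns every treatment-emergent subject whose positives span less than 16 weeks. A test that accepts an NR sample as not positive treats absence of information as evidence that the antibodies disappeared. The error has one direction: it moves subjects from persistent to transient.

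The test matters most at the primary analysis. SAP 6.2 sets the data cut-off at Day 85 of the last subject. For a subject observed only to Day 85, the widest scheduled span runs from Day 15 to Day 85, far short of 16 weeks, so the last assessment alone decides the class.

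For boosting, numerator and denominator should cover the same samples. If the numerator stops earlier, a subject can be counted at risk on the strength of a follow-up sample that is not allowed to show the event. ADA is a named secondary endpoint, and these categories are tabulated by dose level or cohort.

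**Working it through.** **1. Final sample NR.** Inputs: the validity rule and the two definitions in SAP 16.3, and ADA sampling on Days 15, 29, 43, 85, 127 and 169, then every 12 weeks, plus the 30-day follow-up visit.

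Take a subject negative at baseline and on Days 15 and 29, positive on Days 43 and 85, with an NR sample at follow-up.

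- Span: 85 − 43 + 1 = 43 days, below 16 × 7 = 112 days.
- As written: the last assessment is NR, which is not positive, so the subject is transient.
- On the last valid result: Day 85 is positive, so the subject is persistent.

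More generally, take all positive/negative patterns on Days 15, 29, 43 and 85 with at least one positive, followed by NR at an illustrative Day 115 follow-up. There are 2⁴ − 1 = 15. The longest span is 85 − 15 + 1 = 71 days, so the 16-week condition never applies. The 2³ = 8 patterns that are positive on Day 85 change from transient to persistent; the other 7 are transient either way. This counts patterns and is not an expected frequency.

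**2. Boosting window.** Inputs: the follow-up visit is 30 ± 5 days after the last dose (Protocol 7.1.4.1), that is, days 25 to 35. Protocol 7.7 schedules an ADA sample there and, apart from retreated subjects, none at the End-of-Treatment visit. Protocol 8.5.3.1 ends the on-treatment period 30 days after the last dose, or the day before new anticancer drug therapy if earlier.

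- Treatment taken to end at the last dose: 0 of the 11 permitted follow-up days count.
- Protocol on-treatment period: days 25 to 30 count (6 of 11) unless new anticancer drug therapy has started; days 31 to 35 (5 of 11) do not.
- The denominator, and the treatment-emergent category: all 11 days count.

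The numerator and denominator windows differ on either reading.

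**3. The 16-week cut-off (minor).** 127 − 15 = 112 days = 16.0 weeks as a plain difference, or 113 days = 16.14 weeks with the +1 of SAP 9.3.3. Among scheduled sampling days through Day 337, this is the only pair that visit windows can carry across the cut-off. For the every-2-weeks cohorts, Protocol Table 1-1, footnote 1 allows "A time window of up to 3 days before or 1 day after the scheduled visit day". For the weekly cohort, Table 1-2 allows ±1 day on Day 15 and −3/+1 on Day 127.

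With offsets x on Day 15 and y on Day 127, the span is 112 + y − x, plus 1 under SAP 9.3.3.

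| Cohort | Span with +1 | Below 112 with +1 | Below 112 without +1 |
|---|---|---|---|
| Every 2 weeks | 109 to 117 days | 6 of 25 | 10 of 25 |
| Weekly | 109 to 115 days | 6 of 15 | 9 of 15 |

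With +1, the class changes only when y − x ≤ −2, so on-schedule visits give persistent. These are counts of permitted combinations, not probabilities.

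**The case against.** The strongest reply on the NR rule is that an assessment can reasonably be read as one that gave a valid result: the section defines validity, and the denominators rely on it. The phrase grouping missing and NR results with non-positive ones concerns baseline only, so it does not itself settle how a final NR is treated. Both points are fair. But the definitions do not carry the word valid, and literal code would class the subject as transient.

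It is also fair that little depends on the categories. The endpoint is serum titers, Protocol 8.5.3.2 plans a listing of results and titers, and SAP 16.3 lists individual ADA results for every ever-positive subject, so a reader could spot such a case. No dose decision uses the split. This limits the importance but does not make the summary table right.

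A reader might draw three stronger conclusions that the documents do not support:

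- *That boosting at the 30-day visit is ignored.* Protocol 8.5.3.1 extends the on-treatment period to 30 days after the last dose, and SAP 15.2 uses the same limit for treatment-emergent adverse events. On that reading most of the visit window is covered. What remains is an undefined and mismatched window. Boosting is also separate from persistence, since it applies only to subjects positive at baseline.
- *That visit timing decides the class in 40% of subjects, or 60% in the weekly cohort.* Those shares omit the +1 of SAP 9.3.3 and treat combinations as equally likely. Only subjects first positive on Day 15, last positive on Day 127 and not positive at the last assessment are affected.
- *That the transient/persistent split is the main clinical descriptor of immunogenicity.* Neither document says so.

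**Conclusion.** Two corrections to SAP 16.3 are justified. First, the transient rule as written labels a subject transient when the last valid result is positive, the positive span is under 16 weeks and the final sample is NR. This rests on the literal text. Second, the boosted numerator uses an undefined period narrower than its own denominator: it excludes follow-up samples on days 31 to 35 or after new anticancer drug therapy under the protocol's definition, and all follow-up samples if treatment ends at the last dose.

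The 16-week boundary needs only a stated convention. The documents do not show that scheduled dates, or dropping the +1, would be more correct.

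The expected number of affected subjects cannot be derived, because ADA incidence, the NR rate and the distribution of visit days are not given. One subject is 1/6 = 17 percentage points of a cohort of 6, or 1/3 = 33 of a cohort of 3, if all are in the denominator. The effect is confined to a descriptive secondary immunogenicity table in about 21 to 24 subjects; the primary endpoints are untouched.

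**What to change.** In the SAP 16.3 category table:

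1. Replace last assessment by *last valid ADA result* in both the transient and the persistent definitions. A positive last valid result then makes the subject persistent, which agrees with the SAP's own treatment of "a positive evaluation at the last assessment".
2. In the boosted definition, replace the on-treatment restriction by *at any valid post-baseline assessment, including the 30-day Safety Follow-up Visit*, so that numerator and denominator match.
3. Add one sentence stating whether the 16-week span uses actual or scheduled dates and whether the +1 of SAP 9.3.3 applies. If scheduled dates are chosen, say how a span ending at the follow-up visit is measured, because that visit is tied to the last dose and has no scheduled study day.

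The cost is a few phrases in the SAP and the matching derivation code. No new samples or design changes are needed.
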